5.2 EXCLUSION CRITERIA

Participants are excluded from the study if any of the following criteria apply:

Medical Conditions

- 1. Pregnant (positive pregnancy test) or lactating women.
- 2. Co-infection with other pathogens such as hepatitis A (HAV), hepatitis C (HCV), hepatitis D (HDV), hepatitis E (HEV), or human immunodeficiency virus (HIV).
- 3. History of cirrhosis or current evidence of significant liver fibrosis or cirrhosis (F3 or above on liver biopsy, ≥ 7.4 kPa on transient elastography, > 1.32 m/s on acoustic radiation force impulse [ARFI] elastography, or > 3.13 kPa on magnetic resonance [MR] elastography or > 7.1 kPa on 2D-shear wave elastography [2D-SWE]), or decompensated liver disease (e.g., ascites, hepatic encephalopathy). Liver biopsy or transient elastography/ARFI/MR result must be obtained within 6 months prior to randomization.

- 4. History of or suspicion of hepatocellular carcinoma (HCC) (e.g., elevated α -fetoprotein [AFP] levels, suggestive lesions on abdominal ultrasound or other imaging, etc.).
- Thyroid disease poorly controlled on prescribed medications or clinically relevant abnormal thyroid function tests (thyroid-stimulating hormone [TSH], free triiodothyronine [FT3], free thyroxin [FT4]) at screening, as judged by the Investigator.
- 6. Clinically significant disease other than CHB that, in the opinion of the Investigator, makes the participant unsuitable for the study.
- 7. Pre-existing cardiac disease that in the opinion of the investigator would increase the risk for the patient to participate to the study.
- 8. History of alcohol abuse and/or drug abuse within one year of randomization.
- 9. History of having received (in the last 6 months) or currently receiving any systemic anti-neoplastic (including radiation) or immunosuppressive (including biologic immunosuppressors) or immune modulating treatment (including non-biological oral immune modulating drugs; e.g., methotrexate > 25 mg per week, azathioprine > 3.0 mg/kg/day or 6-mercaptopurine > 1.5 mg/kg/day) for malignant or non-malignant disorders.
- Currently taking, or have received within 3 months of Day 1, systemic
 corticosteroids at a high-dose (e.g., 40 mg prednisolone per day for) > 7 days, or a
 low-dose (e.g., 20 mg prednisolone per day) for > 14 days.

Diagnostic Assessments

- 11. Electrocardiogram (ECG) with clinically significant abnormalities, including QTcF interval (QT corrected using Fridericia's formula) ≥450 msec for males and ≥470 msec for females at screening.
- 12. Laboratory parameters at screening:
 - a) Hemoglobin < lower limit of normal (LLN); platelets < LLN; international normalized ratio (INR) > 1.1 × ULN.
 - b) Albumin < 3 g/dL; total bilirubin > ULN (exception: Gilbert's disease).
 - c) Positive results for anti-mitochondrial antibodies (AMA > 1:80), antinuclear antibody (ANA > 1:80), anti–smooth muscle antibody (ASMA > 1:40), or anti-thyroperoxidase antibodies (a-TPO ≥ ULN).
 - d) White blood cell count < 2500 cells/mm³; neutrophil count < 1500 cells/mm³
 (< 1000 cells/mm³ if considered a physiological variant in a participant of African descent).
 - e) Glomerular filtration rate (GFR; using Modification of Diet in Renal Disease [MDRD])<60 mL/min.
 - f) Positive test for drugs of abuse (including recreational drugs) and/or positive alcohol test at screening. For positive cannabinoids test, the eligibility is at the Investigator's discretion.

Prior/Concurrent Clinical Study Experience

- 13. Previous treatment with an investigational agent for HBV within 6 months prior to screening.
- 14. Unable to comply with any drugs or nutrients listed in prohibited medications and prohibited food sections in the respective treatment arm appendix.
- 15. Known hypersensitivity to any excipients of the study drug.

Please refer to Table 3 in Appendix 6 for the list of applicable inclusion/exclusion criteria and check the respective appendix of each treatment arm for additional treatment-related inclusion/exclusion criteria that must be checked in all participants before randomization if any arm requiring additional exclusion criteria is open for recruitment.

All eligibility decisions are made by the Investigator. The Medical Monitor is available to the Investigator to answer any medical questions.

5.3 LIFESTYLE CONSIDERATIONS

Alcohol intake should be strongly discouraged, but limited intake is allowed, when in agreement with the Investigator. Refer to the respective appendix of each treatment arm for treatment-related details.

5.4 SCREEN FAILURES

Screen failures are defined as participants who consent to participate in the clinical study but are not subsequently entered in the study.

If a subject fails an inclusion/exclusion criterion due to a transient and non-clinically significant condition at screening, the Investigator may repeat the relevant assessment(s) within the screening period. If the subject fails a second time, they will be classified as a screen failure.

Re-screening is allowed for participants who were screened in the study and met all study inclusion/exclusion criteria within both screening visits (Day -56 to -7 and Day -14 to -7) but failed to be subsequently randomized within the screening period. In order to re-screen such a subject, all inclusion and exclusion criteria should be re-evaluated and all applicable screening assessments repeated. With the exception of the eye examination if randomization will occur within 6 months from the last examination.

In some instances, participants who did not meet the inclusion/exclusion criteria during the screening period (including those following re-testing) and were registered as screen failures in the IxRS system, can be re-screened and will be treated as new participants provided the new screening informed consent form (ICF) signature date is at least 6 months after the previous screen failure date. In order to re-screen such a subject, all

inclusion and exclusion criteria should be re-evaluated and all applicable screening assessments repeated.

Re-screened participants are required to sign a new ICF and will be assigned a new screening number.

The Investigator will maintain a screening log to record details of all participants screened and to confirm eligibility or record reasons for screening failure.

6. STUDY TREATMENTS

Study treatment is defined as any investigational treatment(s), marketed product(s), or medical device(s) intended to be administered to a study participant according to the study protocol.

All IMPs required for completion of this study will be provided by the Sponsor. All non-investigational medicinal products (NIMPs) required for completion of this study will be either provided or reimbursed by the Sponsor.

6.1 TREATMENTS ADMINISTERED

Refer to the respective appendix of each treatment arm for details.

6.2 PREPARATION/HANDLING/STORAGE/ACCOUNTABILITY

Study drug packaging will be overseen by the Roche clinical trial supplies department and will bear a label with the identification required by local law, the protocol number, drug identification, and dosage.

The packaging and labeling of the study medication will be in accordance with Roche standard and local regulations.

The investigational site will acknowledge receipt of IMPs and confirm the shipment condition and contents. Any damaged shipments will be replaced.

Upon arrival of the IMPs at the site, site personnel will complete the following:

- Check the IMPs for damage.
- Verify proper identity, quantity, integrity of seals, and temperature conditions.
- Report any deviations or product complaints to the Study Monitor upon discovery.

The Investigator or delegate must confirm that appropriate temperature conditions have been maintained during transit for all study treatment received and any discrepancies are reported and resolved before use of the study treatment.

Only participants enrolled in the study may receive study treatment and only authorized site staff may supply or administer study treatment. All study treatments must be stored

in a secure, environmentally controlled, and monitored (manual or automated) area in accordance with the labeled storage conditions with access limited to the Investigator and authorized site staff.

The Investigator is responsible for study treatment accountability, reconciliation, and record maintenance (i.e., receipt, reconciliation, and final disposition records).

IMPs will either be disposed of at the study site according to the study site's institutional standard operating procedure (SOP) or returned to the Sponsor with the appropriate documentation. The site's method of IMP destruction must be agreed upon by the Sponsor. Local or institutional regulations may require immediate destruction of used IMP for safety reasons. The site must obtain written authorization from the Sponsor before any IMP is destroyed, and IMP destruction must be documented on the appropriate form.

Further guidance and information for the final disposition of unused study treatment are provided in the Pharmacy Manual.

6.3 MEASURES TO MINIMIZE BIAS: RANDOMIZATION AND BLINDING

6.4 TREATMENT COMPLIANCE

The qualified individual responsible for dispensing the study treatment will prepare the correct study treatment according to the randomization schedule. This individual will write the date dispensed and participant number on the study treatment vial/bottle label and on the Drug Accountability Record. This individual will also record the study treatment number received by each participant during the study.

Each participant will be provided with a paper and/or an electronic medication diary. It is mandatory that each treatment which is self-administered is recorded in the diary, including any modified/missed doses and their reason. Participants must bring completed drug diaries to each visit during the treatment period to be reviewed by the investigator. Each modified/missed dose must be recorded on the eCRF.

6.4.1 Method of Treatment Assignment

This is an open-label study; however, the specific treatment to be taken by a participant will be assigned using an Interactive Voice/Web Response System (IVRS/IWRS). Potential selection bias due to the open-label status of this study will be reduced by the use of central randomization. The site will contact the IVRS/IWRS prior to the start of study treatment administration for each participant. The site will record the treatment assignment on the applicable electronic case report form (eCRF), if required.

This study will use an adaptive stratified sampling method, minimization, for randomization. The first participant will be allocated a treatment at random; the treatment allocated to the next participant will be dependent on the characteristics of those

participants already enrolled with the aim of minimizing the imbalance within each stratification level (screening HBsAg level < 1000 IU/mL vs. ≥ 1000 IU/mL). A minimum of 12 participants per arm with a screening HBsAg level of < 1000 IU/mL is required.

For treatment arms starting at later study time points, the ongoing central randomization to the control arm ensures any potential selection bias is minimized, specifically, if there is only one treatment arm recruiting. The subsequent randomization ratio will depend on the number of experimental treatment arms that are open for recruitment with the condition that no more than 1/6th (0%-17%) of the participants will be randomly allocated to the control arm at a given time. Additionally, for subsequent arms the proportion of HBsAg level < 1000 IU/mL or $\ge 1000 \text{ IU/mL}$ within each treatment arm will be maintained as closely as possible to the first combination treatment arm.

Randomization will also take into account arm-specific exclusion criteria of actively enrolling arms. Participants will be ineligible for a specific arm if they meet any of the exclusion criteria outlined for that arm (please see arm specific appendix). The arm-specific exclusion criteria will specifically relate to safety due to the molecule's Mechanism of Action (MOA); therefore, it is not expected to introduce any bias in the efficacy outcome. However, a flexible cap will be added to the other recruiting arm(s) to control the number of participants being randomized to these arms, in order to maintain the element of randomization to the end of the randomization period.

Expansion arm/s (of a treatment arm that shows promising efficacy outcomes): If only one expansion arm is open at the time, eligible participants will be enrolled in that arm. If two or more expansion arms are enrolling at one time, a fixed permuted block randomization will be used to allocate participants to arms.

As an additional step to minimize bias, on-treatment and off-treatment virology data (HBV DNA excluded) will not be routinely available to sites, and they will be stored in a restricted data repository for access by the IMC Biometricians. During study conduct, aggregated summaries of data will only be available to the IMC and SOC. However, other members of the Sponsor may have access to aggregated summaries/virology data to assist with decision making, as considered necessary by the IMC.

6.5 CONCOMITANT THERAPY

Any medication or vaccine (including over-the-counter [OTC] or prescription medicines, approved dietary and herbal supplements, nutritional supplements) and any non-medication interventions (e.g., individual psychotherapy, cognitive behavioral therapy, smoking cessation therapy, rehabilitative therapy) used by a participant from 30 days prior to screening until the follow-up visit must be recorded in eCRF along with reason for use, dates of administration (including start and end dates), and dosage information (including dose and frequency).

The Medical Monitor should be contacted for advice if there are any questions regarding concomitant or prior therapy. All concomitant medications should be reported to the Investigator and recorded on the Concomitant Medications eCRF. All therapy and/or medication administered to manage adverse events should be recorded on the Adverse Event eCRF.

6.5.1 Permitted Therapy

Participants who use oral contraceptives, hormone-replacement therapy, or other maintenance therapy should continue their use. Paracetamol/acetaminophen, at doses of up to 2 g/day, is permitted for use any time during the study.

6.5.2 Administrative Structure

For information on the Internal Monitoring Committee (IMC) and *Scientific Oversite Committee* (SOC), please refer to Appendix 1.

6.5.3 **Prohibited Therapy**

In general, the following concomitant medication are prohibited during the study:

- Systemic immunosuppressive drugs, immunomodulators, cytotoxic or chemotherapeutic agents, radiation therapy.
- Systemic high-dose corticosteroids (e.g., > 40 mg prednisolone per day) > 7 days or low-dose corticosteroids (e.g., > 20 mg prednisolone per day) for > 14 days.

Unless otherwise stated in the respective appendix of each treatment arm, prescribed concomitant medication is not prohibited during the study. Participants should refrain from taking non-prescription medication, unless it is considered necessary by the Investigator.

6.6 DOSE MODIFICATION

Please refer to the respective appendix for each treatment arm for dose modification or interruption guidelines.

6.7 TREATMENT AFTER THE END OF THE STUDY

The Sponsor does not intend to provide study treatment or other study interventions to participants after conclusion of the study or any earlier participant withdrawal.

6.8 CRITERIA FOR STOPPING NUCLEOSIDE ANALOGUE

Participants who complete the treatment period will stop NUC *therapy* if laboratory results on samples taken at end-of-treatment or at any of the follow-up visits show:

- ALT<1.25× baseline values, AND
- HBV DNA<LLOQ or<20 IU/mL, AND
- negative HBeAg, AND
- HBsAg <100 IU/mL and $\geq 1 \log_{10} IU/mL$ decline from baseline or HBsAg loss.

These criteria for stopping NUCs do not apply to any patients who have discontinued study drug prematurely for any reason.

7. DISCONTINUATION OF STUDY TREATMENT, PARTICIPANT DISCONTINUATION/WITHDRAWAL FROM THE STUDY AND LOST TO FOLLOW-UP

Participants have the right to voluntarily discontinue study treatment or withdraw from the study at any time for any reason.

An excessive rate of withdrawals (either participants discontinuing study treatment or withdrawing from the study) can render the study non-interpretable. Therefore, unnecessary withdrawal of participants should be avoided and efforts should be taken to motivate participants to comply with all the study-specific procedures as outlined in this protocol.

Details on study and site closures are provided in Appendix 1.

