During the course of the study, participants will be monitored to ensure that HBV DNA suppression is maintained. Participants who experience HBV DNA breakthrough while having NUC therapy, with or without administration of a combination of NMEs, will need to attend a clinic visit for repeat testing. If the HBV DNA level is confirmed to be more than 100 IU/mL or 1-log above nadir, the participants will be assessed for evidence of drug resistance using sequencing and potentially phenotyping. The sample will also be

used to determine the HBV genotype and a pharmacokinetic (PK) sample will be collected.

Finally, participants who have been taken off the combination of NMEs and the NUC therapy will have their HBV DNA monitored every 2 weeks *for the first 3 months and monthly thereafter* until 48 *weeks* post-EOT. If the HBV DNA level rises, participants will be monitored and *managed in case of* virological relapse *as per Section 8.3.8.2* and an unscheduled blood sample will be collected for potential characterization of the HBV genome and where feasible phenotyping (see Sections 8.7.2 and 8.7.3).

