8.3.8.2 Management of Virological Relapse

Participants who have discontinued all study treatments (NME combinations) including NUC therapy should be followed up every 2 weeks for first 12 weeks, thereafter monthly up to week 48 of the follow up period to enable early detection of HBV DNA rebound and appropriate management of virological relapse.

In addition, participants with HBV DNA > 20 IU/mL but < 2,000 IU/mL in follow-up, should undergo monitoring every two weeks.

Participants who discontinue all study treatment (NME combination and NUC therapy for the treatment arms or NUC therapy for the NUC control arm) and subsequently experience virological relapse (HBV DNA > 2,000 IU/mL) during the follow-up period will undergo weekly monitoring: an unscheduled blood sample will be collected for potential HBV genome characterization and where feasible phenotyping.

NUC therapy *should* be restarted in the following scenarios:

- *HBV DNA* > 20,000 *IU/mL* (regardless of other biochemical parameters or ALT values)
- HBV DNA > 2,000 IU/mL and ALT > 1.5 x ULN
- HBV DNA > 2,000 IU/mL and ALT ≤ 1.5 x ULN and if the retest (central or local laboratory) of HBV DNA performed within 1 week after availability of the initial results from the central laboratory confirms HBV DNA > 2,000 IU/mL (regardless of ALT values or other biochemical parameters)
- Immediately restart treatment in participants with clinically significant signs of decreasing liver function based on laboratory findings (e.g., INR, direct bilirubin) or clinical assessments (e.g., ascites, hepatic encephalopathy) regardless of HBV DNA or ALT levels.

For these additional unscheduled monitoring visits, the following laboratory assessments should be performed using the unscheduled lab kit: hematology, chemistry, coagulation, GLDH, urinalysis, HBV serology, HBV DNA quantitative, Total HBsAg, HBcrAg, and HBV RNA quantitative.

Note: The guidance for the management of virological relapse (frequency of monitoring, laboratory assessments, NUC restarting rules) described in this section should be followed in conjunction with the guidance for the management of elevated ALT levels described in Section 8.3.8.3.

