Appendix 7-Table 2 Schedule of Activities for NUC Control Arm (cont.)

- ^b Blood pressure, pulse rate, respiratory rate and body temperature obtained at least 5 minutes after participant has been in supine/sitting position.
- ^c Historical liver biopsy or transient elastography/ARFI/MR/2D- shear wave elastography [2D-SWE] results obtained within 6 months prior to randomization are also acceptable. During screening transient elastography/ARFI/MR/2D-SWE are acceptable.
- ^d Autoantibodies refer to ANA, AMA, ASMA, and a-TPO.
- ^e Alcohol and drugs of abuse screen to be conducted according to local procedures.
- f Pregnancy testing for females of childbearing potential only; serum test at screening, urine test at other visits. If urine pregnancy test is positive, the pregnancy must be confirmed by a serum test.
- g HbA1c should be assessed only at screening.
- h If not collected at Day 1, samples for clinical genotyping and HBV RNA sequencing can be collected at any subsequent time point. The sample for HBV RNA sequencing aims at determining the HBV genotype. The HBV genotype may also be inferred using alternative approaches, such as serovariant determination.
- ⁱ Total HBsAg refers to HBsAg measured post-dissociation of HBsAg/HBsAb complexes/components of HBsAg.
- ightharpoonup HBV DNA sequencing will be collected in case of virological breakthrough/relapse, blood sample to be collected up to 6 times.
- ^k Plasma PK samples for NUC to be collected at pre-dose. During the PK assessments for VB/VR visits, only one predose sample is required for collection, no other additional time points should be collected.
- ¹RBR samples collected only from RBR-consenting participants.
- ^m Pre-treatment, only serious adverse events should be reported.
- ⁿ Participants who achieve HBsAg loss during treatment or during follow-up will discontinue NUC.
- o Additional post-treatment visits for participants who discontinued NUC at Week 48. If participants discontinue NUC later in the follow-up additional visits *should* be scheduled with a frequency of every 2 weeks for the first three months and every 4 weeks up to week 48 of follow-up period.
- ^p Participants who permanently discontinue study treatment will need to attend an unscheduled/early termination visit.
- ^q Visit window may be extended to +6 weeks in extreme circumstances such as pandemic, natural disasters, supply chain disruption, outbreak of hostilities.

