ECG									х		х		
Abdominal ultrasound									х		х		
Alfa-fetoprotein									х		х		
Alcohol and drugs of abuse screen ^c													х
Pregnancy test ^d		х		х		х	х	х	х	х	х		х
Thyroid function tests									х		х		
Hematology	х	х	х	х	х	х	х	х	х	х	х	х	х
Chemistry	х	х	х	х	х	х	х	х	х	х	х	х	х
Coagulation	х	х	х	х	х	х	х	х	х	х	х	х	х
GLDH	х	х	х	х	х	х	х	х	х	х	х	х	х
Urinalysis	х	х	х	х	х	х	х	х	х	х	х	х	х
HBV serology (HBsAg, HBeAg, anti-HBs, anti-HBe)	х	х	х	х	х	х	х	х	х	х	х	х	х
HBV DNA quantitative ^I	х	х	х	х	х	х	х	х	х	х	х	х	х
Total HBsAg ^e		х		х		х		х	х		х	х	
HBcrAg		х		х		х		х	х		х	х	
Total anti-HBc quantitative						х			х		х		
HBV RNA quantitative		х		х		х		х	х		х	х	
HBV DNA sequencing												х	
Plasma PK (siRNA)													

Appendix 9-Table 4 Schedule of Activities for siRNA (100 mg or 200 mg) + NUC Treatment Arm (Follow-up Period) (cont.)

						Foll	ow-up pe	eriod					VB/VR	ET/UV i
	Week	2	4	6	8	10	12	16	20	24 ^k	36	48		-
	Day	14 (±3)	28 (±3)	42 (±3)	56 (±3)	70 (±3)	84 (±7)	112 (±7)	140 (±7)	168 (±7)	252 (±7)	336 (±7)		
Plasma PK (NUC) ^f													х	
Plasma ADA (siRNA)							х			х	х	х	х	Х
Liver biopsy ^j										х				
RBR 9													х	
Diary review		х	х	х	х	х	х	х	х	х	х	х	х	х
Adverse events & concomitant medications h		Х	х	х	х	х	х	х	х	х	х	х	х	х

ADA=anti-drug antibodies; ARFI = acoustic radiation force impulse; DNA = deoxyribonucleic acid; ECG = electrocardiogram; ET=early termination; GLDH = glutamate dehydrogenase; HAV/HBV/HCV/HDV/HEV = hepatitis A/B/C/D/E virus; HBcrAg = hepatitis B core-related antigen; HBeAg = hepatitis B e antigen; HBsAg = hepatitis B surface antigen; HIV = human immunodeficiency virus; MR = magnetic resonance; NUC = nucleos(t)ide analogue; PK = pharmacokinetics; RBR = Research Biosample Repository; RNA = ribonucleic acid; ; siRNA= short interfering ribonucleic acid; Total HBsAg = post-dissociation of HBsAg/HBsAb complexes/components of HBsAg; VB/VR = virological breakthrough/relapse; UV = unscheduled visit.

Note: If participants discontinue NUC later in the follow-up, additional visits *should* be scheduled with a frequency of every 2 weeks for the first three months and every 4 weeks up to week 48 of follow-up period.

^a Full physical examination at screening and at the end-of-treatment. Limited symptom-directed physical examination at other visits and as clinically indicated.

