ADA = anti-drug antibodies; DNA = deoxyribonucleic acid; ECG = electrocardiogram; ET=early termination; FNA = fine needle aspirate; GLDH = glutamate dehydrogenase; HBV = hepatitis B virus; HBcrAg = hepatitis B core-related antigen; HBeAg = hepatitis B e antigen; HBsAg = hepatitis B surface antigen; NUC = nucleos(t)ide analogue; PD-L1 = programmed death ligand-1; PK = pharmacokinetics; RBR = Research Biosample Repository; RNA = ribonucleic acid; siRNA= short interfering ribonucleic acid; Total HBsAg = post-dissociation of HBsAg/HBsAb complexes/components of HBsAg; VB/VR = virological breakthrough/relapse; UV = unscheduled visit.

Note: If participants discontinue NUC later in the follow-up, additional visits should be scheduled with a frequency of every 2 weeks for the first three months and every 4 weeks up to week 48 of follow-up period.

- ^a Full physical exam at screening and at the end-of-treatment. Limited symptom-directed physical exam at other visits and as clinically indicated.
- ^b Blood pressure, pulse rate, respiratory rate, and body temperature obtained at least 5 minutes after participant has been in supine/sitting position.
- ^c Alcohol and drugs of abuse screen to be conducted according to local procedures.
- ^d Pregnancy testing for females of childbearing potential only; serum test at screening, urine test at other visits. If urine test is positive, it must be confirmed by a serum test.
- ^e Total HBsAg refers to HBsAg measured post-dissociation of HBsAg/HBsAb/components of HBsAg.
- ^f No plasma PK samples are collected during the follow-up period. During the PK assessment for VB/BR visits, only one pre-dose sample is required for collection.
- ^g RBR samples collected only from RBR-consenting participants.
- ^h Cytokine panel (e.g., INF-α, IP-10, IL-1, IL-6, IL-10, IFN-γ, and TNF-α).
- ¹ PBMC at selected sites only, two collections: Follow-up Days 84 and 168. The exact days of collection may be adjusted by the Sponsor based on emerging data.
- ^j Optional sub-study FNA at selected sites only.
- ^k Participants who discontinue study treatment prematurely will be required to attend an unscheduled/early termination visit.

Appendix 13-Table 9 Schedule of Activities for siRNA + PD-L1 LNA + NUC Treatment Arm – 24 and 36 Week (Follow-up Period) (cont.)

¹ Visit window may be extended to +6 weeks in extreme circumstances such as pandemic, natural disasters, supply chain disruption, outbreak of hostilities.

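### Section 6.8 names no last qualifying visit, so a follow-up Week 48 sample can direct a NUC stop with no relapse-monitoring visit left

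*Protocol*

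**What the plan says.** Protocol 6.8 is directive. Participants who complete the treatment period are to stop NUC "if laboratory results on samples taken at end-of-treatment or at any of the follow-up visits show" all of the following: ALT below 1.25 times baseline, HBV DNA below quantification or below 20 IU/mL, negative HBeAg, and either HBsAg loss or HBsAg below 100 IU/mL with at least a 1 log10 decline. The only exclusion is premature discontinuation of study drug. For the control arm, Appendix 7-Table 2 footnote n is equally open-ended: "Participants who achieve HBsAg loss during treatment or during follow-up will discontinue NUC".

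Off-NUC monitoring has a fixed end. Under Protocol 8.3.8.2, participants off all study treatment including NUC "should be followed up every 2 weeks for first 12 weeks, thereafter monthly up to week 48 of the follow up period". Section 4.2.3 (HBV DNA Monitoring) has the same end point. For those who stop later in follow-up, Appendix 7-Table 2 footnote o asks for extra visits "scheduled with a frequency of every 2 weeks for the first three months and every 4 weeks up to week 48 of follow-up period", and the notes in Appendices 9, 10, 12 and 13 agree. Weekly monitoring after a relapse is also confined to the follow-up period.

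Section 6.4.1 adds that "on-treatment and off-treatment virology data (HBV DNA excluded) will not be routinely available to sites".

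**The concern.** The protocol treats the weeks after a NUC stop as the period that needs the closest watch. The Version 7.0 rationale for changing 8.3.8.2 is early detection and prompt management of relapse, so that participants do not decompensate. Yet 6.8 also lets the last visit of the study trigger a stop. A participant who first qualifies on that sample would come off suppressive therapy with no protocol HBV DNA or ALT check afterwards, and the restart rules in 8.3.8.2 could not be applied within the study.

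What is at stake is participant safety and clear conduct at study end, not the efficacy comparison.

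**Working it through.** The plan gives no figure to reproduce here, so the check is whether Week 48 can trigger a stop and what monitoring would follow.

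**Can the Week 48 sample trigger a stop?** Yes. The follow-up schedules of the non-terminated arms (Appendix 7-Table 2, 9-Table 4, 10-Table 4, 12-Table 5 and 13-Table 9) all mark chemistry (ALT), HBV DNA and HBV serology (HBsAg and HBeAg) at Week 48. All four criteria in 6.8 can therefore be assessed on that visit's samples.

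**How many monitoring visits remain?** Rule from 8.3.8.2 and the late-stop notes: every 2 weeks for 12 weeks, then every 4 weeks, ending at follow-up Week 48. Visits are counted from the triggering sample.

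| Triggering visit | Two-weekly visits | Four-weekly visits | Total |
|---|---|---|---|
| EOT | 2, 4, 6, 8, 10, 12 | 16, 20, 24, 28, 32, 36, 40, 44, 48 | 6 + 9 = 15 |
| Week 24 | 26, 28, 30, 32, 34, 36 | 40, 44, 48 | 6 + 3 = 9 |
| Week 36 | 38, 40, 42, 44, 46, 48 | none | 6 + 0 = 6 |
| Week 48 | none | none | 0 |

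**Could the two-weekly block run beyond Week 48?** The text does not support this. Follow-up is fixed at 48 weeks (4.1), a participant completes the study at the last visit (4.4), and no schedule contains a later visit.

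**Does another section fill the gap?** No. Section 8.3.1 does not require active adverse-event monitoring after the last follow-up visit, and 6.7 plans no sponsor-provided treatment or intervention after the study. Section 8.3.3.1 follows events that are already open, which does not supply HBV DNA or ALT tests to find a new relapse. The SAP is silent.

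**How far does it reach?**
- Arms: 9 listed in Appendix 6-Table 1, minus 2 terminated arms whose participants stay on NUC, leaves 7.
- Scheduled follow-up visits for a participant still on NUC: 11 in the NME arms (Weeks 2, 4, 6, 8, 10, 12, 16, 20, 24, 36, 48) and 4 in the control arm (Weeks 12, 24, 36, 48). Week 48 is one of these in each case.
- Primary endpoint: the latest sample is at 24 + 6 = Week 30 under the extended window.

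**Is Week 36 a workable limit?** Week 36 is Day 252 (±7) and Week 48 is Day 336 (±7).
- Nominal gap: 336 − 252 = 84 days = 12 weeks.
- Shortest: 329 − 259 = 70 days = 10 weeks.
- Longest: 343 − 245 = 98 days = 14 weeks.

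Laboratory turnaround is not stated. If the stop follows the sample by 1 to 2 weeks (assumed), a Week 36 trigger leaves 11 to 10 nominal weeks off NUC under observation, and a Week 48 trigger still leaves none.

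**The case against.** The strongest reply is that a Week 48 stop would hardly ever happen. The tests are run centrally, so results would normally arrive after the participant has completed the study. Sites do not routinely see HBsAg or HBeAg, two of the four criteria, so someone holding restricted data would have to prompt the stop. The participant must also have missed the criteria at EOT and at every earlier follow-up visit (10 in the NME arms, 3 in the control arm). Significant fibrosis and cirrhosis are excluded, and the amendment summary describes the tighter restart rules as precautionary, not prompted by safety findings in this study. In practice the treating physician would decide.

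The point about rarity stands. The rest makes the event less likely but does not cancel the instruction: 6.8 still orders the stop, and nothing passes the decision or the results to anyone. Local care may well detect a relapse, but the protocol does not arrange it.

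A second reply is that Week 36 is a preference and that one hand-over sentence would suffice. It is true that Week 36 leaves no four-weekly phase, and no relapse-timing data in the documents show that 12 weeks is enough. A Week 24 limit or longer follow-up would give more cover. But participants still on NUC have no scheduled visit between Weeks 36 and 48, so a Week 36 limit removes only one scheduled trigger, the one with no monitoring behind it. A hand-over sentence alone, with the directive left in place, would still order the stop.

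**Conclusion.** The concern holds. Read as written, 6.8 and footnote n can direct a NUC stop on the Week 48 sample with none of the monitoring that the protocol requires after any other stop: 0 visits, against 6 after a Week 36 trigger and 15 after EOT. It applies to 7 of the 9 listed arms.

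The visit counts assume nominal visit dates and a stop on the date of the sample; a later stop only shortens the remaining time. The number of participants exposed cannot be derived from the documents and is probably very small. No efficacy conclusion changes. It should be fixed because the gap concerns the safety of participants taken off suppressive therapy and takes only a few sentences to close.

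**What to change.** - **Section 6.8 and Appendix 7-Table 2 footnote n:** state that follow-up Week 36 is the last visit whose sample can trigger a protocol-directed NUC stop. It is the latest scheduled visit that keeps the full nominal 12-week two-weekly phase. Participants who first qualify later stay on NUC at study end, and the decision passes to the treating physician.
- **Section 6.4.1:** add an exception releasing these participants' HBsAg and HBeAg results to the site after their Week 48 visit, together with the monitoring and restart guidance of 8.3.8.2. Without it the physician would lack two of the four criteria.
- **SAP:** no edit. Table 5 stands, and the listing in 4.6.1 of participants who met the criteria but did not stop follows the amended 6.8.

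The cost is one sentence in 6.8, the same limit in one footnote, and one sentence in 6.4.1. Ethics and authority approval is needed as locally required (Appendix 1, 2.3.1), so it belongs in the next amendment. There are no added visits, no change in sample size and no change to the primary analysis. The downside is that a few late qualifiers, possibly including some with HBsAg loss, do not stop NUC within the study.
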